## II. Specific Aims

Overview of Trial Design—The overall goal for these trials is to provide the data necessary for the design of definitive clinical trials. Specifically, we aim to test recruitment feasibility, the feasibility of POC electrolyte measurement and POC-directed management of the dialysis prescription, and to provide preliminary estimates of effect size with manipulation of UF rate, dialysate K, and dialysate HCO3. We will perform two related, randomized cross-over trials; Study A- dialysate interventions trial, consisting of 2 dialysate potassium interventions and 2 dialysate bicarbonate interventions (4 total cross-over interventions); and Study B-ultrafiltration rate intervention trial, consisting of 2 separate ultrafiltration rate strategies.

The central hypothesis underlying Study A and Study B is that the risk of clinically significant arrhythmias in HD patients can be reduced by altering components of the dialysis prescription.

**Aim 1—To test the feasibility and safety of POC-guided dialysate prescription adjustment and the feasibility of limiting UF rate in HD patients.** The current studies will pilot our educational strategies and the dialysate potassium, dialysate bicarbonate and UF intervention strategies to test their feasibility in a multi-center setting. They will test the hypothesis that  $\geq 80\%$  adherence with proposed interventions is feasible, and that the safety need for unscheduled dialysis or severe abnormalities in potassium and bicarbonate will be minimal.

**Aim 2—To assess recruitment feasibility and retention rate for trials combining ILR insertion to monitor arrhythmia and interventions using POC-guided dialysis prescription or UF rate manipulation.** Screen failures and retention rates will be captured and analyzed. Whether recruitment rates  $\geq 1$  patient per month and retention rate  $> 90\%$  are achievable in each study will be tested.

**Aim 3—To refine effect estimates of the change in monthly CSA duration during Study A (dialysate potassium intervention to maximize vs. minimize intradialytic potassium removal) and Study B (aggressive vs. conservative ultrafiltration rate).** Refining estimates of change in CSA with each pair of interventions will provide key information necessary for design of definitive trials. Whether CSA decreases with minimization of potassium removal, alkalosis limitation and UF rate minimization will be tested.

**Substudy Aim—To assess the relationship between Reveal LINK EKG morphology and pre-dialysis electrolyte concentrations.**

### III. Subject Selection

These trials will test the impact of dialysate K/HCO3 and UFR on CSA. Subjects from study-affiliated dialysis units will be screened.

#### Inclusion Criteria:

- a. Maintenance hemodialysis therapy for end-stage renal disease
- b. Age 18-85 years
 

\*To enrich the trial population for arrhythmia events, subjects between 18-40 years old will be required to have at least one of the following: history of congestive failure, diabetes, coronary or peripheral vascular disease, or arrhythmia.
- c. > 30 days since dialysis initiation
- d. Ability to provide informed consent

#### Exclusion Criteria:

- a. Expected survival <6 months—to allow trial completion
- b. Renal transplant, transfer to home or peritoneal dialysis, or to non-study HD facility anticipated within 6 months
- c. Prisoners or cognitive disability preventing informed consent
- d. Pregnancy. A pregnancy test will be required for women of child bearing potential prior to enrollment. A pregnancy test will not be required for women past the age of child-bearing potential >55 years old, women with a history of surgical sterilization, or for women <55 years of age who have not had a menses within the past 12 months. Women with child bearing potential will be required to use a highly effective method of contraception for the duration of the study. Highly effective methods include hormonal contraception, barrier methods or abstinence.
- e. Condition which in the opinion of the investigator increases risk of local infection with ILR placement such as skin conditions, known immune dysfunction or frequent infections suggestive of immune dysfunction.
- f. Bleeding disorder that cannot be reversed for ILR placement. For patients on coumadin INR value >2.5 within 72 hours of ILR placement. For patients on novel oral anti-coagulants (NOAC)—inability to hold NOACs for 24 hours before and after the procedure.
- g. Existing pacemaker, implantable monitor or defibrillator which precludes device placement
- h. Chronic, persistent atrial fibrillation

#### Additional Inclusion/Exclusion

##### Criteria: Study A Exclusions:

- a. Hemoglobin <8 g/dL—only 100 µL is needed for each POC test, but safety is improved by avoiding serial phlebotomy when anemia is severe.
- b. Serum K >6.5 or <3.5 mEq/L within 30 days—severely hyperkalemic or hypokalemic patients are not suitable for testing the proposed algorithms since both algorithms call for similar prescriptions at the extremes of physiologic values.

**Study B Inclusion Criteria:**

- a. It is required that subjects have an interdialytic weight gain necessitating an UF rate of  $\geq 13$  mL/kg/hour of dialysis to achieve the target post-dialysis weight in  $\geq 6$  dialysis sessions in the month prior to enrollment.

## **IV. Subject Enrollment**

### ***Participant Recruitment and Screening***

Participants at dialysis units affiliated with investigators will be pre-screened for eligibility. No one who cannot legally give consent will be approached. In addition to active screening of dialysis unit rosters by study personnel, informational handouts and brochures may be disseminated at affiliated dialysis units in order to allow for interested participants to learn about the study and to contact the study investigator if interested. All study material must be approved by local IRBs before dissemination to potential study participants.

Dialysis unit labs, medical records at the investigator's institution, and treatment or history records at local dialysis units will be reviewed to assess eligibility for enrollment. No study-specific testing is required to confirm eligibility. To introduce the study to potential subjects, a care provider known to the patient will inquire about the subject's interest in learning about research studies and request permission for study staff to approach the patient and present the study. Alternatively, flyers will be posted at dialysis units advertising Study A and B. Flyers will include options for potential subjects to indicate their willingness to be contacted by the study team and will provide contact information so that patients can directly contact the study team to learn about the trials. Each participant's treating nephrologist will be contacted to assess suitability for enrollment prior to consent.

Once preliminary eligibility is confirmed, informed consent will be obtained by a qualified investigator or study site designee during an in-person visit. This visit may take place either at the local dialysis unit or at the investigator's institution, according to investigator and participant preferences. In the event that an in-person consent cannot be obtained, electronic consent through the NYU HIPAA compliant software REDCap will be made available. Study personnel will notify current patients of any changes made to the consent by phone or email including instructions for completing the electronic consent. Currently enrolled subjects may take as long as needed to review these changes, and make a decision to continue on study. For women of childbearing potential, a serum pregnancy test will be performed to determine final eligibility.

Subjects will be compensated for time and expenses for scheduled study visits, up to a total of \$300 (6 scheduled study visits). Subjects in both studies (A and B) will be compensated \$150 at study visit 4 and study visit 8. He/she and their insurance company will not be charged for the cost of the study related procedures.

### ***Early Withdrawal of Participants***

#### **When and How to Withdraw Participants**

Early withdrawals will be discouraged and participants who are not willing to continue the intervention will be encouraged to remain in the study and continue study evaluations. However, participants may be withdrawn from the study under the following circumstances that have the potential to compromise patient autonomy or safety:

- a. Pregnancy
- b. Withdrawal of consent
- c. Allergy to or documented intolerance to ancillary study medications for implant procedure (e.g. lidocaine, versed, xylocaine, or other medications used for local anesthetic or conscious sedation)
- d. Non-compliance with dialysis schedule compromising ability to follow serum potassium on a monthly basis
- e. Organ transplantation
- f. Change to a different dialysis modality
- g. Prolonged hospitalization
- h. Transfer to non-participating dialysis unit
- i. Incarceration

[figure not shown]
#### **Data Collection and Follow-up for Withdrawn Participants**

In the case of withdrawal, every attempt will be made to obtain consent to continue to follow patients for the occurrence of mortality, hospitalizations, and other safety signals via telephone or in-person contact with participants, relatives, and dialysis unit staff and records until scheduled end of follow-up.

Participants will be deemed as lost to follow-up after  $\geq 3$  attempts have been made to contact the patient via their preferred means of contact (telephone or email),  $\geq 1$  attempt has been made to contact the patient via their secondary means of contact, and  $\geq 1$  attempt to contact next of kin is unanswered.

## **V. Description of Study Procedures**

Two related, randomized cross-over trials will be performed; Study A-a dialysate interventions trial, consisting of 2 dialysate potassium interventions and 2 dialysate bicarbonate interventions (4 total cross-over interventions); and Study B- an ultrafiltration rate intervention trial, consisting of 2 separate ultrafiltration rate strategies. A total of 20 patients will be enrolled in each trial. An overview of the study design is illustrated in **Figure 5 below**.

**ILR Intervention**— Consent and ILR placement at the local site will be followed by a one-month baseline observation period. ILR placement will be followed by wound check visits at 1 week and 1-month post implant. Outpatient insertion of ILR by study cardiologists will occur within 4 weeks of enrollment. Reveal LINQ™ (Medtronic) implantable monitors will be utilized.

**Arrhythmia Detection**—Detection of clinically significant arrhythmias (CSA) will be achieved using implantable loop monitors (ILR) inserted at the start of each trial. ILR tracings will be batch analyzed by study cardiologists blinded to randomized treatment. Tracings from ILR-detected events meeting automated, validated detection criteria for bradycardia, asystole, AF, sustained or non-sustained ventricular tachycardia (VT) will be manually reviewed at least once every two weeks. Clinically significant arrhythmias will be defined on the basis of arrhythmias likely to lead to sudden cardiac arrest or serious morbidity and mortality and will include atrial fibrillation (AF), asystole lasting  $\geq 3$  seconds, bradycardia  $\leq 40$  beats per minute lasting  $\geq 6$  seconds, sustained VT  $\geq 130$  beats per minute lasting  $\geq 30$  seconds, and any sudden cardiac arrest. Positively adjudicated CSA will be entered into a study database and coded according to arrhythmia type, date and duration.

**Dialysate Interventions Trial (Study A)**—This trial will test the impact of dialysate K and HCO3 on CSA. After a month of usual care, subjects will cross-over in random order to four month-long periods using alternative approaches to algorithm-specified manipulation of dialysate K or HCO3 guided by POC-obtained laboratory testing prior to each dialysis. There will be a one-week washout with usual care between each intervention period. Randomization sequences will be balanced with respect to treatments to minimize impact of sequence or carryover effects on outcomes. Algorithms tested will compare **a) Minimization of dialysate-serum potassium gradient vs. maximization of potassium removal** (preferential use of high potassium dialysate to minimize gradient vs. low K dialysate to maximize removal); and **b) Alkalosis avoidance vs. acidosis avoidance** (preferential use of lower dialysate HCO3 concentration vs. higher dialysate HCO3). Subjects and investigators will be blinded to the intervention in use. HD nurses and staff will obtain POC chemistry results prior to each HD session and adjust the prescription for dialysate potassium or HCO3 as dictated by the algorithm. Since dialysate prescription changes must be entered manually, dialysis staff cannot be blinded to the algorithms, but they will not assess endpoints or be otherwise involved in interpretation of study data.

Whole blood (100  $\mu$ L) will be obtained by dialysis staff when the catheter, fistula or graft is accessed prior to each HD session during the K and HCO3 intervention periods. Blood will be drawn into a non-heparinized syringe and added to the i-STAT cartridge for immediate testing—a process similar to routine blood glucose testing during HD. Blood will be immediately tested on the i-STAT according to the manufacturer's protocol. (Alternatively blood may be drawn into heparinized tubes, mixed by inversion, and tested within 10 minutes). Results are saved on the device, printed, and can be entered directly to the study data-base.

**Potassium (K) Intervention**—This intervention will test whether minimizing intradialytic fall in serum K **Dialysate Potassium Intervention Algorithm** by using higher K dialysates to minimize serum-dialysate K gradients reduces the incidence of CSAs compared to an approach prioritizing lower K dialysate to reduce the incidence of hyperkalemia. This will be achieved by utilizing an algorithm which couples POC-testing with the choice of one of two dialysate K concentrates (2 or 3 mEq/L potassium, **Table [left]**) that are widely available in dialysis clinics. Although there is potential equipoise regarding use of very low K dialysates (1 mEq/L) in hyperkalemic patients, 1K dialysate is either restricted or not available in the majority of US outpatient HD units.

POC Serum K (mEq/L)	Dialysate K (mEq/L)	Gradient (mEq/L)
K removal maximization Strategy		
<4	3	0
4-5.0	3	1-2
5.1-6.3	3	2.1-3.3
$\geq 6.4$	2	$\geq 4.4$
Gradient-Minimization Strategy		
<4	3	0-1
4-5k	2	2-3
5.1-6.3	2	3.1-4.3
$\geq 6.4$	2	$\geq 4.4$

substudy. Participants in the substudy will be asked to press the button on the REVEAL patient assistant device to automatically trigger their implanted REVEAL LINQ ILR to record an EKG tracing each time their blood drawn is drawn by the dialysis staff prior to dialysis for POC testing. Patients will also be asked to perform a full transmission upon returning home from dialysis to assure an adequate length of EKG tracing is obtained before and after the patient assistant button is pressed at dialysis.

**Bicarbonate (HCO3) Intervention**—The bicarbonate intervention is designed to compare an algorithm designed to avoid acidosis (by use of lower dialysate HCO3) with one that avoids alkalosis (by use of higher dialysate HCO3). As shown in the **Table (right)**,

POC-HCO3 results will be obtained prior to each HD session and will inform the selection of the dialysate HCO3 concentration. As with potassium, POC-testing allows dialysate HCO3 concentration to be matched according to serum HCO3 and has analogous advantages in terms of safety, achieved gradient, and potential analyses, compared to a design using fixed dialysate concentrations. The algorithm has been designed based on published data on the expected post dialysis increases in serum HCO3 and overall time-averaged serum HCO3 expected from any given combination of pre-dialysis serum and dialysate HCO3 concentrations. As shown in the table, excellent separation of dialysate and serum HCO3 concentrations are expected.

Dialysate Bicarbonate Intervention Algorithm				
POC HCO 3 (mEq/L)	Dialysate HCO 3 (mEq/L)	Gradient (mEq/L)	Expected Change in post HD HCO 3	Expected Time Avg HCO 3
Acidosis Avoidance				
<20	40	≥20	[contact]-18	[contact]	33	6-8	negligible rise	26
≥28	26	≤ -2	negligible decrease	26
Alkalosis Avoidance				
<20	36	≥16	[contact]	7-11	[contact]	-1-3	negligible rise	24
≥28	20	≤ 16	negligible decrease	26

**Overview of Ultrafiltration (UF) Trial- Study B**—The UF rate intervention will use identical inclusion/exclusion criteria as the dialysate Intervention trial with a few exceptions. Subjects are required to have an interdialytic weight gain necessitating an UF rate of ≥13 mL/kg/hour of dialysis to achieve the target post-dialysis weight in ≥6 dialysis sessions in the month prior to enrollment. This criterion is necessary to achieve separation in UF rates between the aggressive and restricted UF rate periods. Conversely, there will be no exclusions on the basis of baseline hemoglobin or serum potassium concentration since point of care testing of electrolytes is not be required and the UF intervention is not expected to impact serum potassium concentration.

After ILR placement, subjects will crossover between two UF rate interventions: 1) UF rate-restricted dialysis, in which UF rates are limited to a maximum of 10 mL/kg/hr for the duration of the session 2) UF rate-unrestricted dialysis. It is anticipated that patients with large interdialytic weight gains in the UF rate-restricted intervention may not achieve their target post-dialysis weight during the prescribed treatment time. In order to prevent progressive volume overload and the need for additional HD sessions to manage volume gains in this scenario, subjects will crossover weekly between the restricted

and unrestricted UF interventions. This weekly crossover accomplishes two important goals: First, it reduces safety concerns by ensure that any volume gained due to limiting the UF are constrained to one week and promptly addressed with unlimited UF the following week. Second, it increases separation between UF rates in the two interventions, since a higher UF-rate will be needed to address any weight and volume gains resulting from UF-rate restriction.

Investigators will be blinded. Subjects will not be blinded as it is not feasible to blind them to the goal UF and post-dialysis weight (typically self-measured); HD staff will have access to the algorithm in order to adjust UF rate accordingly. Following a one-month baseline observation period with usual care, subjects will undergo 4 weeks of each UF intervention administered in alternating weeks as described above, for a total study duration of 12 weeks. Data will be aggregated and results compared using a full month of data for each intervention.

**End of Study Procedures**—In order to maximize recruitment efficiency and the significant investment in undergoing ILR implantation, patients completing one study will be given the option of continuing to eligibility screening and enrollment for the alternate study. If subjects consent to both Study A and Study B, then the baseline observation period for the second study may be less than 1 month. Those refusing or ineligible will be offered ILR explanation.

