## Study Summary

[figure not shown]
Title	Reducing Arrhythmia in Dialysis by Adjusting the Rx Electrolytes/Ultrafiltration
Short Title	RADAR
Protocol Number	
Phase	Pilot
Methodology	
Randomized, Crossover, Blinded, Multi-arm
 
Interventions:
 
Implanted Loop Recorder
 
Potassium/Bicarbonate Trial (Study A)
 
Ultrafiltration Trial (Study B)

Study Duration	24 months
Study Center(s)	
Duke University Medical Center (DUMC)
 
New York University Langone Health (NYU)-coordinating site receiving funding from the NIH with dialysis unit located at Lower Manhattan Dialysis Center ([name]).

Objectives	
 
• To obtain pilot data on adherence, safety and barriers to implementation of proposed interventions.
 
• To obtain pilot data on recruitment feasibility and subject retention.
 
• To obtain pilot data to estimate the potential effect sizes of proposed interventions.
 

Number of Participants	
40 (20 in each of two interventions)
 
(60 participants enrolled with 40 expected to reach randomization. Because patients have the option of enrolling in both study A and B it is possible that the total number of devices required will be less than 40.)

Diagnosis and Main Inclusion Criteria	Dialysis-dependent end-stage renal disease
Study Product/Intervention, Route, Regimen	
Study A: Potassium/Bicarbonate Four-Arm Crossover
 
Potassium (K) Removal Maximization strategy, 1 month (lower dialysate K)
 
Potassium (K) Gradient-Minimization Strategy, 1 month (higher dialysate K)
 
Acidosis Avoidance, 1 month (higher dialysate bicarbonate)
 
Alkalosis Avoidance, 1 month (lower dialysate bicarbonate)
 
Study B: Dialysis Ultrafiltration Rate (UFR) Two-Arm Crossover
 
UFR <math>\leq</math>10 ml/kg/hr, 1 month
 
UFR as needed, 1 month

Ancillary Products:	
LINQ™ (Medtronic) Implantable Cardiac Loop Recorder (Carelink System)
 
i-STAT (Abbott)- Study A only

Duration of administration	LINQ™: 3-6 months Study A: 4 months Study B: 2 months

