**Figure 6**  
Reveal LINQ

of their transmitter during the programmed daily transmission time. Battery life is approximately 3-years, and devices are conditionally approved for use with MRI. The incidence of device related complications is minimal and includes infection (1.2%), device migration, and pain at the implant site (<1%). Since the device is leadless, the vast majority of infections are local and treatable with oral antibiotics or device extraction (an in-office procedure). Bacteremia is an extremely rare complication. To wit, out of 66 HD patients implanted in MiD, there was only 1 definite infection and one possible implantation-related infection. Neither were bacteremic and both were successfully treated with antibiotics without device extraction. Thus, MiD data supports device safety and minimal risk of bacteremia or serious device associated infection in HD patients, regardless of dialysis access type. Out of an abundance of caution patients with history of multiple infections or immune deficiencies will nevertheless be excluded from participation in Study A and B

**Point-of-care Testing (POC)**—POC testing will be performed at each dialysis session with dialysate K or HCO3 adjusted accordingly by algorithm. POC testing allows for real-time recognition of extreme excursions in HCO3 and K and immediate dialysate manipulation as needed to maximize safety. It also ensures maximization of differences in serum-dialysate K gradients between tested algorithms while avoiding use of low K dialysate when serum potassium is already low. Further, POC at each session provides the necessary data to

**Figure 7** Abbott i-STAT system and cartridges

evaluate the achieved gradient between serum and dialysate with each strategy, to analyze association of the achieved gradient with arrhythmia, and to specifically assess for interaction between ambient serum and dialysate potassium in terms of CSA risk. Finally, POC testing allows evaluation of the extent to which POC-guided prescription differs from care in which dialysate choice is based on monthly measurement alone as assessed by the % of sessions in which management differs.

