### **Study A Intervention - Dialysate K/HCO3 Trial: Monthly Visits:**

Study treatment to be started on the 1st Monday/Tuesday following the Week 4 Reveal Visit. There will be 4 crossover groups and subjects will rotate monthly through all the treatment groups in a random blinded order. Prior to initiation of all HD sessions, subjects will receive POC testing via the Abbott i-STAT, which requires approximately 100uL of blood. This testing, along with their treatment arm assignment, will drive the dialysate prescription for that specific HD session (see figures/tables further below). The 4 cross-over groups are listed below:

- i. Potassium Removal Maximization strategy, 1 month (low dialysate K)
- ii. Potassium Gradient-Minimization Strategy, 1 month (high dialysate K)
- iii. Acidosis Avoidance, 1 month (low dialysate bicarbonate)
- iv. Alkalosis Avoidance, 1 month (high dialysate bicarbonate)

There will be a 1-week washout period between subsequent interventions and during this week, participants' dialysate prescription will be determined by their dialysis physician. Dialysis treatment records will be reviewed at least monthly and standard of care labs will be recorded at visits 5 through 8.

Subjects enrolled in the optional substudy will press the button on the REVEAL patient assistant device to automatically trigger their implanted REVEAL LINQ ILR to record an EKG tracing each time their blood drawn is drawn by the dialysis staff prior to dialysis for POC testing. Subjects will also record a full transmission upon returning home from dialysis with the Carelink Transmitter.

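### Study A's potassium algorithm table has its two strategy headings reversed; if units follow it as printed and arms are analysed by name, the potassium contrast takes the wrong sign

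*Combined protocol and SAP*

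**What the plan says.** Four places in the protocol define the potassium arms in the same direction:

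- Study Summary: "Potassium (K) Removal Maximization strategy, 1 month (lower dialysate K"; gradient minimization is paired with higher dialysate potassium.
- Section V, Dialysate Interventions Trial (Study A): "preferential use of high potassium dialysate to minimize gradient vs. low K dialysate to maximize removal".
- Section V, Potassium (K) Intervention, prose: the question is whether minimizing the fall in serum potassium "by using higher K dialysates to minimize serum-dialysate K gradients reduces the incidence of CSAs compared to an approach prioritizing lower K dialysate".
- Section V, Study A Intervention, Monthly Visits: "Potassium Removal Maximization strategy, 1 month (low dialysate K"; gradient minimization is again the high-potassium arm.

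Section I supplies the physiology behind this: a lower-potassium bath removes more potassium.

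The Dialysate Potassium Intervention Algorithm table sits beside the third of these statements. Its first block is headed "K removal maximization Strategy" and assigns bath 3, 3, 3, 2 mEq/L for point-of-care (POC) potassium <4, 4–5.0, 5.1–6.3 and ≥6.4. Its second block, headed as gradient minimization, assigns 3, 2, 2, 2.

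The table is meant to be used at the chairside: "HD nurses and staff will obtain POC chemistry results prior to each HD session and adjust the prescription for dialysate potassium". On blinding, "Subjects and investigators will be blinded to the intervention in use". Section VI (Statistics and Analysis) compares arrhythmia duration between the potassium arms by strategy name, and Aim 3 asks a directional question: whether arrhythmia falls when potassium removal is minimized.

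**The concern.** The table gives each strategy the baths that the rest of the protocol gives to the other one. It is also the only potassium rule with thresholds, so a unit cannot set a session's bath from the prose alone.

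If units follow the printed headings and the analysis uses arm names, the Aim 3 potassium contrast has the wrong sign. A benefit of the higher bath would be reported as a benefit of the lower one. The intervention-specific potassium safety events in Section VI (severe abnormalities, unscheduled dialysis or admission) would likewise be credited to the wrong strategy.

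Section VI says the pilot exists to supply the mean and SD of the change for planning definitive trials, so the direction attached to that mean matters even though the analyses are exploratory.

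**Working it through.** **1. Inputs, as printed in the algorithm table**

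| POC K (mEq/L) | Block headed removal maximization: bath; gradient | Block headed gradient minimization: bath; gradient |
|---|---|---|
| <4 | 3; 0 | 3; 0–1 |
| 4–5.0 | 3; 1–2 | 2; 2–3 |
| 5.1–6.3 | 3; 2.1–3.3 | 2; 3.1–4.3 |
| ≥6.4 | 2; ≥4.4 | 2; ≥4.4 |

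**2. Reproducing the gradient column.** Gradient = POC K − bath.

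- Bath 3: 4 − 3 = 1 and 5.0 − 3 = 2; 5.1 − 3 = 2.1 and 6.3 − 3 = 3.3.
- Bath 2: 4 − 2 = 2 and 5.0 − 2 = 3; 5.1 − 2 = 3.1 and 6.3 − 2 = 4.3.
- Top band: 6.4 − 2 = 4.4 in both blocks.

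Every row from POC K 4 upward reproduces, so baths and gradients agree within each block and it is the headings that conflict with the text. The <4 rows do not fit: both use bath 3, so both gradients should be <1, yet the table prints 0 in one and 0–1 in the other.

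**3. Direction.** Bath under maximization minus bath under minimization, across the four bands:

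- as printed: 0, +1, +1, 0;
- as the four text statements require: 0, −1, −1, 0.

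The arms differ only at POC K 4.0–6.3, and throughout that band the difference runs the wrong way by 1 mEq/L.

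**4. Effect on the named contrast.** Let δ be the true change between the two strategies and f the fraction of subjects treated by the printed headings in both potassium periods. Then

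expected named contrast = (1 − f)δ + f(−δ) = (1 − 2f)δ.

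| f | 0 | 0.25 | 0.5 | 0.75 | 1 |
|---|---|---|---|---|---|
| Multiple of δ | 1 | 0.5 | 0 | −0.5 | −1 |

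At f = 1 the sign reverses while size and SD are unchanged. Between 0 and 0.5 the contrast is diluted, at 0.5 it is zero, and above 0.5 it is reversed. The documents give no value for f. The Section VI efficacy model has a site main effect but no treatment-by-site term, so it would not itself display two sites working to opposite rules.

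**5. Effect on the SD under mixed use.** Mixing +δ and −δ adds 4f(1 − f)δ² to the variance of the change, at most δ² (f = 0.5). The SD then rises by √(1 + d²), where d = δ / SD of change. Assume the SD of 1765 minutes quoted in Section VI (Effect Estimates) is a monthly between-subject SD, and take the changes stated there as δ:

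| Within-subject correlation r | SD of change = 1765 × √(2(1 − r)) | Stated change (min) | d | √(1 + d²) |
|---|---|---|---|---|
| 0.9 | 789 | 140 | 0.18 | 1.02 |
| 0.7 | 1367 | 370 | 0.27 | 1.04 |
| 0.5 | 1765 | 470 | 0.27 | 1.03 |

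The worst-case inflation is therefore about 1.02 to 1.04. The stated changes are smaller than what 20 subjects could detect at 80% power from that SD. Using d = (1.96 + 0.84)/√20 ≈ 0.63 instead gives √(1 + 0.63²) ≈ 1.18. The sign and size of the mean are the main exposure.

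**The case against.** The strongest reply is that this is a heading error in one table, and the units may be working from a correct sheet that is not in the documents. The text around the table is also damaged in the extracted copy: the table title falls inside a sentence, a stray fragment follows it, and the <4 rows disagree. Displaced headings cannot be fully excluded, so the source page must be checked first. However, the agreement of bath and gradient within each block shows that the rows are intact, and nothing in the protocol supports the headings as printed.

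A second reply is that any harm is recoverable. That stands for uniform use of the printed headings, where relabelling restores the result. It also stands for any consistent misreading that the treatment records can identify.

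A third reply is that existing steps could expose the swap. Section VI plans to relate adherence to site. The DSMB appendix (Closed Session) has adherence reviewed by masked group. Section I (Point-of-care Testing) says session-level testing provides the data to "evaluate the achieved gradient between serum and dialysate with each strategy". Any of these might reveal it, but none is described as a check of delivered bath against arm label. Adherence scored against the algorithm need not show the problem, because a unit that follows the printed table exactly can be scored as adherent.

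A reader might go further and infer that the two sites delivered opposite rules, that adherence scoring could not detect this, or that the SD would be badly inflated. The documents do not support these readings. No unit is shown using a different version, the steps just listed could flag one that did, and on the protocol's own figures the SD effect is small. A reader might also turn the width of the 4.0–6.3 band into a count of wrongly treated sessions, but the documents give no distribution of POC potassium from which to do so.

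**Conclusion.** The concern holds. The headings of the only potassium threshold rule contradict four other statements in the protocol, and over the whole range where the arms differ the contradiction is a 1 mEq/L gradient in the wrong direction. It needs correcting because staff act on this table at each session and the analysis goes by arm name.

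The consequences are conditional. Uniform use of the printed headings reverses the sign of the potassium contrast and misattributes potassium safety events, with size and SD intact. Mixed use, which is possible but not shown, gives (1 − 2f) times the true contrast.

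It should not be read as a finding that the pilot's potassium results are reversed: the documents do not show which version was used. Confidence is high for the conflict in the text, subject to the source page, and is not claimed for what was delivered. Because the analyses are exploratory, the exposure is to planning data and safety attribution rather than to a confirmatory result.

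**What to change.** 1. Check the source page of the protocol and the algorithm sheet actually used in the units.
2. Swap the two headings. For POC K <4, 4–5.0, 5.1–6.3 and ≥6.4, removal maximization should read bath 3/2/2/2 and gradient minimization bath 3/3/3/2. Correct both <4 gradients to <1.
3. Issue one controlled algorithm sheet to all units.
4. From existing treatment records, have an unblinded person who does not assess endpoints tabulate delivered bath at POC K 4.0–6.3 by site, period and arm label. If the printed headings were used, label each randomized period by the rule delivered, without reclassifying single sessions.
5. As a related wording correction, with no delivery effect claimed: the Bicarbonate Intervention paragraph and the Monthly Visits list pair acidosis avoidance with lower dialysate bicarbonate. Align them with the Study Summary, the Study A design text and the bicarbonate algorithm table, where acidosis avoidance is the higher-bicarbonate arm.

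The cost is a protocol clarification, one reissued sheet and one tabulation from records already reviewed at least monthly. No extra patients, visits or procedures are needed.
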